3.3.2 Nucleocapsid-binding antibody seroconversion

Nucleocapsid (N)-binding antibody seroconversion is defined as a positive N-binding antibody result after the first dose in subjects without serological evidence of previous infection (determined by negative N-binding antibody) at Visit 1 and without previous virological evidence of infection (determined by negative NAAT results at Screening and Visit 1).

The surveillance period will start after the first dose for subjects in Cohort 1, Cohort 4, and Cohort 6 in Part B until the earliest of the following events:

- Date of the first positive N-binding antibody test.
- or when the subject's end of trial occurs.

3.3.3 **CD4+ and CD8+ T-cell responses (Ex vivo ELISpot)**

T cell-mediated immune responses after one, two, or three doses of the multivalent vaccine BNT162b2 (B.1.1.7 + B.1.617.2), or one booster dose of the monovalent vaccine BNT162b2 (B.1.1.7), or one booster dose of BNT162b2 (B.1.617.2), at 30 µg will be analyzed. Cell-mediated immune (CMI) responses will be measured by interferon γ (IFNγ) enzyme-linked immuno spot (ELISpot).

T-cell responses of the trial subjects will be analyzed for both CD4+ and CD8+ T-cells specific for the SARS-CoV-2 reference strain full length spike (FL-S), SARS-CoV-2 FLS B.1.1.7 (“Alpha variant”), and SARS-CoV-2 FLS B.1.617.2 (“Delta variant”). The SARS-CoV-2 S protein will be tested using two peptide pools (Spike protein pool 1 [SP1]: N-terminal half; Spike protein pool 2 [SP2]: C-terminal half) for each variant. Hereinafter, “target” refers to the applied experimental stimulus (spike protein pool 1, spike protein pool 2, or the sum of spike protein pools 1 + 2) in the ELISpot readout.

For analysis of responders, the spot counts of the ELISpot assay will be evaluated with the ELISpot data analysis (EDA) tool. In the next steps, these results are checked by subject matter experts, and a final call on presence or absence of T-cell responses is made for each analyzed sample, hereinafter named “expert call”.

3.4 **Baseline and other variables**

3.4.1 **Definition of baseline value and SARS-CoV-2 infection at baseline and post vaccination**

Unless otherwise specified, the last non-missing measurement or sample collected prior to first IMP injection is considered the baseline data for all assessments.

Baseline in immunogenicity analysis:

The baseline value used in the derivation of geometric mean fold rise (GMFR), SR, and difference of SR for Part A, Part B and Part C of the trial is the value before first dose of trial IMP.

Baseline SARS-CoV-2 infection status:

For Part A and Part B, baseline SARS-CoV-2 infection is defined as below:

Positive:

- if any one of the 3 tests, i.e., nucleocapsid-binding antibody seroconversion, central NAAT, or local NAAT, is positive,
- OR
- had medical history (MH) or AE of COVID-19 prior to vaccination.

Negative:

- no MH or AE of COVID-19 prior to vaccination,
- AND
- negative N-binding.

AND

- both local and central NAAT negative or one negative and one missing.

Missing/indeterminate:

- no MH or AE of COVID-19 prior to vaccination,

AND

- no positive test results from any of the 3 tests,

AND

- N-binding missing or both NAAT missing.

Evidence of SARS-CoV-2 infection post vaccination

No evidence of SARS-CoV-2 infection post vaccination for subjects in Part B is defined as subjects who had no serological or virological evidence of SARS-CoV-2 infection (i.e., negative N-binding antibody [serum] result and negative NAAT [oral swab] at all planned visits and any unscheduled visit (up to the 1-month post–Dose 2 blood sample collection for Cohort 6 and 1-month post–trial vaccination blood sample collection for Cohort 1 and Cohort 4) and had no medical history or AE of COVID-19 (up to the 1-month post–Dose 2 blood sample collection for Cohort 6 and 1-month post–trial vaccination blood sample collection for Cohort 1 and Cohort 4)).

No evidence of SARS-CoV-2 infection post vaccination for subjects from Phase III trial BNT162-02 / C4591001 is defined as subjects who had no serological or virological evidence (up to the 1-month post–Dose 2 blood sample collection) of SARS-CoV-2 infection (i.e., negative N-binding antibody [serum] result at the Dose 1 and 1-month post–Dose 2 visits, negative NAAT [nasal swab] at the Dose 1 and Dose 2 visits, and any unscheduled visit (up to the 1-month post–Dose 2 blood sample collection)) and had no medical history of COVID-19.

3.4.2 Trial day and analysis visits

Trial day:

Trial day will be calculated in reference to Day 1, defined as the date of first dose of trial IMP administration. For assessments conducted after Day 1, trial day is calculated as (assessment date – Day 1 date +1). For assessments conducted before Day 1, trial day is calculated as (assessment date – Day 1 date). There will be no Trial Day 0.

Analysis visits:

For clinical safety data summary, lab data, vital signs, electrocardiogram (ECG), and physical exam, the analysis visits post vaccination will be based on the visits reported and validated in the EDC database.

For immunogenicity assays, the sampling windows with grace period specified in [Table 7](#) will be used to define the valid samples to include in the Immunogenicity Analysis Set, and the per protocol sampling windows will be used to define the valid samples to include in the Immunogenicity Analysis Per Protocol Set. See [Table 8](#) for the definitions of the analysis sets.

Table 7. Immunogenicity sampling windows

Visit relative to dose	Window per CTP = Include in (per protocol) Immunogenicity Analysis Set	Additional grace period = No impact on immunogenicity = Include in Immunogenicity Analysis Set	Impact on immunogenicity = Exclude from Immunogenicity Analysis Set Important PD if supporting a primary endpoint. Non-important PD if not supporting a primary endpoint
1 week post dose	8+2 8-10 days	NAP	All OOW
3 weeks post dose	21±3 18-24 days	+/- 2 x days OOW ≥16 to ≤26 days	+/- 3 days and more OOW <16 days or >26 days
1 month post dose	29±3 26-32 days	+/- 7 days OOW ≥19 to ≤39 days	+/- 8 and more days OOW <19 days or >39 days
3 months post dose	85±5 80-90 days	+/- 7 x days OOW ≥73 to ≤97 days	+/- 8 and more days OOW <73 days or >97 days
6 months post dose	180±10 170-190 days	+/- 7 x days OOW ≥163 to ≤197 days	+/- 8 and more days OOW <163 days or >197 days
1 year post dose	360±10 350-370 days	+/- 14 x days OOW ≥336 to ≤384 days	+/- 15 and more days OOW <336 days or >384 days

Grace period will not be applied.

Abbreviations: OOW = out of window; NAP = not applicable; PD = protocol deviation.

The following conversion rules will be used to convert days to months and days to years:

- 1 month = 30.4375 days
- 1 year = 365.25 days

For subjects in Part A and Part B (Cohort 1 and Cohort 4) of the trial, time at IMP Dose 1 (Vax 3) since Dose 2 of BNT162b2 (Vax 2) in days = (Date of IMP Dose 1 - Date of BNT162b2 vaccine Dose 2) +1. BNT162b2-experienced subjects have received BNT162b2 vaccine (30 µg, two-dose regimen) in either a clinical trial (e.g., BNT162-02/C4591001) or as part of the governmental vaccination programs.

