Abbreviations: AE = adverse event; AESI = AE of special interest; ECG = electrocardiogram; e-diary = electronic diary or an equivalent application; EOT = end of trial; FU = follow-up; h = hour(s); IMP = investigational medicinal product; mon = month(s); N-binding = nucleocapsid-binding; NAAT = nucleic acid amplification-based test; SAE = serious AE;

SARS-CoV-2 = the virus leading to COVID-19; SoA = schedule of activities; Vax = vaccination (i.e., IMP injection); wk = week(s); WOCBP = women of childbearing potential; yr = year(s).

**Table 5: Schedule of events for Part B, Cohort 6; three doses of BNT162b2 (B.1.1.7 + B.1.617.2) in COVID-19 vaccine-naïve subjects**

Activity	Visit 0	Visit 1	Visit 2	Visit 3	Visit 4	Visit 5	Visit 6	Visit 7 i	Visit 8 i	Visit 9/ EOT	Early term.	COVID-19
Visit description	Screening	Pre-Vax 1 h	1 wk Post-Vax 1 FU	Pre-Vax 2 h	1 wk Post-Vax 2 FU	1 mon Post-Vax 2 FU	6 mon Post-Vax 2 FU & Pre-Vax 3 h	1 wk Post-Vax 3 FU	1 mon Post-Vax 3 FU	1 yr Post-Vax 2 FU m or 6 mon Post-Vax 3 FU		Ad hoc
Days relative to last dose	-7 to -1	1	8+2	21±3	8+2	29±3	182±10			365±10		
Day (relative to Visit 6)								8+2	29±3	180±10		
Collect informed consent	X											
Assess inclusion/exclusion criteria compliance	X	X (review)										
Collect demographic and medical history	X	X (update)										
12-lead ECG	X	X g	X	X	X		X	X				
Perform clinical assessment (includes 15 mL blood draw and urine collection at Visit 0) a	X	X		X			X					
Record (concomitant) medication j	X	X	X	X	X	X	X o	X	X	X o	X o	X o
Perform urine pregnancy test for WOCBP	X	X		X			X					
Oral swabs for NAAT-based SARS-CoV-2 for screening	X	X b										
Allocation to IMP		X										
IMP injection and assess acute reactions for ≥30 minutes after		X		X			X					

Activity	Visit 0	Visit 1	Visit 2	Visit 3	Visit 4	Visit 5	Visit 6	Visit 7 i	Visit 8 i	Visit 9/ EOT	Early term.	COVID-19
Visit description	Screening	Pre-Vax 1 h	1 wk Post-Vax 1 FU	Pre-Vax 2 h	1 wk Post-Vax 2 FU	1 mon Post-Vax 2 FU	6 mon Post-Vax 2 FU & Pre-Vax 3 h	1 wk Post-Vax 3 FU	1 mon Post-Vax 3 FU	1 yr Post-Vax 2 FU m or 6 mon Post-Vax 3 FU		Ad hoc
Days relative to last dose	-7 to -1	1	8+2	21±3	8+2	29±3	182±10			365±10		
Day (relative to Visit 6)								8+2	29±3	180±10		

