6.2 Secondary endpoints

6.2.1 Immunogenicity endpoints – Part A

6.2.1.1 GMT and GMFR of Reference and VOC specific NT at each specified post-vaccination time point

The number of subjects with valid and determinate assay results for the specified assay at each given dose/sampling time point, GMT, GMFRs, and the associated 2-sided 95% CIs will be provided by Cohort based on Immunogenicity Analysis Set. GMFR will be presented from before vaccination to each specified post-vaccination time point.

Also, bar charts including LLOQ and ULOQ lines and with different color codes for data from subjects according to their N-binding assessment for the respective visit, time point and line plots with mean and 95% CIs over time by Cohort and trial part will be presented for VOC and the reference strains.

The analysis described above will also be performed on Immunogenicity Analysis Per Protocol Set.

6.2.1.2 SR to reference and VOC specific NT at each specified post-vaccination time point

The number and percentage of subjects with SR, including the associated 2-sided 95% CI at each specified post-vaccination time point will be provided by Cohort based on Immunogenicity Analysis Set.

The above analyses will also be performed on immunogenicity per protocol set.

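### SAP Table 7's protocol-window column does not match the protocol for every cohort, and it drops compliant 1-week samples in Part A Cohort 6

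*SAP*

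**What the plan says.** SAP Table 7 has one row per visit relative to dose, common to all cohorts. The first window column is headed "Window per CTP = Include in (per protocol) Immunogenicity Analysis Set" and defines the Immunogenicity Analysis Per Protocol Set. The main Immunogenicity Analysis Set uses "the sampling windows with grace period specified in" the same table. The protocol column gives 8 to 10 days at 1 week, 26 to 32 at 1 month, 170 to 190 at 6 months and 350 to 370 at 1 year. Grace extends the last three to "≥19 to ≤39 days", "≥163 to ≤197 days" and "≥336 to ≤384 days". The 1-week row has no grace: everything out of window is excluded and classed as a protocol deviation, non-important when no primary endpoint depends on it.

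The protocol schedules (Section 1.3) differ by cohort. In Part A Cohorts 2 and 6 (Tables 2 and 3) the visits after Dose 2 are counted from Visit 1, and the Cohort 6 1-week visit after Dose 3 is 8+3 from Visit 6. Part B Cohort 6 (Table 5) uses a row headed "Days relative to last dose", with 182±10 and 365±10 for the two long-term visits.

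For Part A, SAP Section 6.2.1 reports GMT, GMFR and seroresponse by cohort on the main set and adds: "The analysis described above will also be performed on Immunogenicity Analysis Per Protocol Set". SAP Section 6.3.1.1 leaves out ELISpot results that fall outside the Table 7 windows and plans Day 8 boxplots.

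**The concern.** A column that claims to carry the protocol's windows should reproduce them. Where it is narrower and there is no grace, a site can follow the protocol exactly and still have its sample removed and logged as a deviation. Both sets used for the Part A immunogenicity tables are windowed, and no all-available (mITT) analysis is planned for Part A, so no summary table keeps the excluded 1-week results. With about 20 subjects per cohort, a few lost samples are noticeable. The Per Protocol Set also stops meaning what its name says at visits where its windows are not the protocol's. SAP Section 8 does not record any of this as a change from the protocol.

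**Working it through.** **Inputs.** Protocol Section 1.3, Tables 1, 2, 3 and 5; SAP Section 3.4.2, Table 7.

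**Day count.** The SAP rule is "For assessments conducted after Day 1, trial day is calculated as (assessment date – Day 1 date +1", so the dose day is Day 1. That rule is written for the first dose; I apply it to each dose:

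post-dose day = visit day − dose day + 1.

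**Reproducing Table 7.** For Part A Cohorts 1, 3, 4 and 5 (protocol Table 1: 8+2, 21±3, 29±3, 180±10, 360±10) this gives 8–10, 18–24, 26–32, 170–190 and 350–370, exactly the protocol column of Table 7.

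**Other cohorts, with Dose 2 on its target day** (Day 56 in Cohort 2, Day 21 in Part A Cohort 6):

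| Visit | Protocol | Post-dose days | Table 7 protocol column | Lost from main set | Lost from Per Protocol Set |
|---|---|---|---|---|---|
| A Cohort 6, 1 week after Dose 2 | 29+3 | 29−21+1 = 9 to 32−21+1 = 12 | 8–10 | 11–12 | 11–12 |
| A Cohort 6, 1 week after Dose 3 | 8+3 | 8–11 | 8–10 | 11 | 11 |
| A Cohort 2, 1 week after Dose 2 | 63+2 | 63−56+1 = 8 to 65−56+1 = 10 | 8–10 | none | none |
| A Cohorts 2 and 6, 1 month after Dose 2 | 86±3; 51±3 | 86−56+1 = 51−21+1 = 31; 28–34 | 26–32 | none | 33–34 |
| A Cohorts 2 and 6, 6 months after Dose 2 | 238±10; 203±10 | 238−56+1 = 203−21+1 = 183; 173–193 | 170–190 | none | 191–193 |
| A Cohorts 2 and 6, 1 year after Dose 2 | 421±10; 386±10 | 421−56+1 = 386−21+1 = 366; 356–376 | 350–370 | none | 371–376 |
| B Cohort 6, 6 months | 182±10 | 172–192 | 170–190 | none | 191–192 |
| B Cohort 6, 1 year | 365±10 | 355–375 | 350–370 | none | 371–375 |

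The Cohort 6 1-year visit after Dose 2 is the alternative to the 6-month visit after Dose 3.

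**Moving Dose 2 within ±3 days while the visit stays tied to Visit 1.** In Cohort 2 the 1-week visit can then fall from 63−59+1 = 5 to 65−53+1 = 13, so days 5–7 and 11–13 are lost. In Cohort 6 after Dose 2 it runs from 29−24+1 = 6 to 32−18+1 = 15. The later visits widen to 25–37, 170–196 and 353–379, all still inside the grace windows.

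**Sensitivity to the day count.** In elapsed days (no +1) the Cohort 6 window after Dose 2 is 8–11 and only day 11 is lost. The conclusion does not depend on the choice: 29+3 and 8+3 each span four days and Table 7 keeps three, so for a fixed dose day at least one compliant day must be lost. I use the Day 1 count because elapsed days would give 7–9 for the single-dose cohorts and no longer reproduce Table 7. The protocol itself is not uniform: 203−21 = 182 and 386−21 = 365 are the Table 5 targets, which fits elapsed days.

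**The case against.** The strongest reply is that the uniform 1-week window looks deliberate. The grace cell is marked not applicable, and Part A describes its cohorts in relation to one another, so equal timing has value. That is a defensible choice, but it would make the column heading wrong and the departure unrecorded.

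It is also fair that the consequences are small:
- Part A has no hypothesis test. Its secondary immunogenicity estimands are headed as applying to BNT162b2-experienced subjects, and Cohort 6 is vaccine-naïve. The exploratory persistence estimand lists baseline and 1, 6 and 12 months, not 1 week. Cohort 6 is reached only because SAP Sections 6.2.1 and 6.3.1.1 tabulate by cohort and time point.
- Table 7 defines valid samples. A missed window removes a time-point result, not necessarily the subject. Out-of-window samples are still listed under SAP Section 6.5.2.3.
- The SAP does not say how days after a second or third dose are counted, so the exact days lost in Cohort 6 after Dose 2 (11–12 or 11) depend on an assumption.

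A reader might go further and infer that most 1-week samples will be lost. Of all allowed pairs of dose day and visit day, only 11 of 28 (39%) in Cohort 6 after Dose 2 and 9 of 21 (43%) in Cohort 2 fall within 8 to 10 days. The documents do not support reading these as retention rates. The count treats every allowed pair as equally likely, whereas sites aim for the target days. Several pairs are also implausible: 3 of the 17 excluded pairs in Cohort 6 and 6 of the 12 in Cohort 2 fall on post-dose day 7 or earlier, before the evening entry that completes the 7-day diary. Without them the shares are 11/25 (44%) and 9/15 (60%), and these are not predictions either.

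**Conclusion.** The inconsistency is real and minor. For Part A Cohort 6, Table 7 as written removes compliant 1-week samples from both windowed sets: post-dose days 11 and 12 after Dose 2 (day 11 only, in elapsed days) and day 11 after Dose 3. This assumes Dose 2 on Day 21 and, for the stated days after Dose 3, the dose day counted as Day 1.

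Cohort 2 is not on the same footing. Its 1-week window is exactly 8 to 10 days at the target Dose 2 day, so samples are lost only if Dose 2 moves and the visit does not move with it. The later mismatches in Part A Cohorts 2 and 6 and in Part B Cohort 6 affect the Per Protocol Set only.

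A reader might also suspect the primary comparisons. They are unaffected: they use the Part B samples at 3 weeks or 1 month after the first trial dose, where Table 7 and the protocol agree. How many samples are actually lost cannot be derived from the documents.

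**What to change.** Reconcile Table 7 with the protocol schedules by giving cohort-specific values in the protocol-window column, counted from the actual dose date. At a minimum this covers the 1-week visits of Part A Cohort 6 after Doses 2 and 3, the 1-month, 6-month and 1-year visits after Dose 2 in Part A Cohorts 2 and 6, and the 6-month and 1-year visits of Part B Cohort 6. State whether the dose day is Day 1 for every dose, and tie the unmarked note on grace beneath the table to the row it belongs to. When writing the Cohort 6 window after Dose 2, say whether day 8, which is kept now, stays in.

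If the uniform 8 to 10 days is intended, keep it, rename the column, and list the departure in SAP Section 8.

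I would not widen the 1-week grace to admit every possible pair of dose day and visit day. That would put days 5–13 (Cohort 2) or 6–15 (Cohort 6) under one 1-week label, against 8–10 in the single-dose cohorts.

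The cost is a table edit and a rerun of descriptive outputs. The downside is one or two more days of timing spread at the Cohort 6 1-week visits.

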3.4.3 Demographics, medical history, and physical examination

The demographic variables are age at screening (in years), age group for Part B and Part C (18 to 55 years, 56 to 85 years, 18 to 64 years, and 65 to 85 years), sex (Male or Female), childbearing potential (yes or no), ethnicity (Hispanic or Latino, Not Hispanic or Latino, Not Reported and Unknown), race (Black or African American, American Indian or Alaskan Native, Asian, Native Hawaiian or other Pacific Islander, White, Other, Multiracial,

Not reported and Unknown), country, height(cm), body weight(kg), Body Mass Index (BMI (kg/m²), Underweight (below 18.5), Normal weight (18.5 to 24.9), Over weight (25 to 29.9), Obese (30 and above)), and diabetes mellitus (Yes or No), baseline SARS-CoV-2 infection status (Positive or Negative) and Time from the second dose of BNT162b2 (received prior to the trial) to the first trial vaccination (days).

In cases where more than 1 category is selected for race, the subject would be counted under the category “multiracial” for analysis.

For Part C, when the last SARS-CoV-2 infection prior to the IMP dose was diagnosed (time between infection and trial randomization), the number of prior COVID-19 RNA vaccines and time from the last dose of COVID-19 RNA vaccination (received prior to the trial) to trial randomization will be presented.

Medical history (MH) will be categorized according to MedDRA® version 24.0 or higher.

Physical examinations will be performed evaluating any clinically significant abnormalities. Body weight (in kg) and any clinically significant abnormal results will be recorded in the case report form (CRF).

Vital signs (oral body temperature, heart rate, blood pressure [systolic and diastolic]), blood and urine clinical laboratory tests will also be recorded.

3.4.4 Prior/Concomitant medications and concomitant procedures

Prior/concomitant medications and concomitant procedures (including non-drug therapies) will be recorded in the CRF. Medications and procedures will be assigned as being prior to trial IMP, concomitant with IMP based on the start and stop dates of the medication and dosing dates.

If the medication/procedure taken from screening visit and stopped before the date of the first dose of trial IMP, the medication/procedure will be assigned as being prior to trial IMP. Otherwise, if taken after the first dose of trial IMP, the medication/procedure will be assigned as being concomitant with trial IMP.

All medications will be coded using the latest version of World Health Organization (WHO) Drug Dictionary.

3.4.5 Other safety endpoints

12-lead ECG will be recorded before and at 7 days after each IMP injection and any abnormal results will be recorded in the CRF. Clinically significant ECG abnormalities will be captured as AEs.

4 ANALYSIS SETS (POPULATIONS FOR ANALYSIS)

Data for all subjects will be assessed to determine if they meet the criteria for inclusion in each analysis set. All analysis sets will be assessed and documented prior to releasing the database for each cohort.

For all trial parts, analyses of safety endpoints will be performed using the Safety Set. Subjects will be summarized for safety analysis according to the vaccine group they actually received. For Part C, demographic and baseline characteristics, medical history,

and prior medications will be tabulated for all randomized subjects as well. Analyses of primary, secondary and exploratory immunogenicity endpoints will be performed using Immunogenicity Analysis Set, Immunogenicity Analysis Per Protocol Set, and/or All-available Immunogenicity Set (mITT) as specified in Sections 6.1.2, 6.2, and 6.3. For mITT, subjects will be summarized according to the vaccine group to which they were randomized/assigned. The analyses of reactogenicity endpoints (i.e., local reactions and systemic events) will be based on Reactogenicity Set. The definitions of each analysis set are specified below in Table 8.

Table 8. Analysis set

Analysis set	Description
Screened Set	All subjects who signed informed consent.
All Randomized Subjects	All subjects who were randomized to Cohort 7, 8, 9 in Part C
Safety Set	All subjects who received at least one dose of IMP.
Reactogenicity Set	All subjects included in the Safety Set with any e-diary data reported after IMP injection.
Immunogenicity Analysis Set	All eligible randomized/assigned subjects who receive the trial intervention to which they are randomized or assigned, have a valid and determinate immunogenicity result from the blood sample collected within an appropriate window ^a , and have no other important protocol deviations that can confound immunogenicity data ^{c,d} .
Immunogenicity Analysis Per Protocol Set	All eligible randomized/assigned subjects who receive the trial intervention to which they are randomized or assigned, have a valid and determinate immunogenicity result from the blood sample collected within per protocol window ^b , and have no other important protocol deviations that can confound immunogenicity data ^{c,d} .
All-available Immunogenicity Set (mITT)	All randomized/assigned subjects who receive the trial intervention and have a valid and determinate immunogenicity result after the trial intervention.

An important protocol deviation is a protocol deviation that, in the opinion of the sponsor’s clinician, would materially affect assessment of immunogenicity, e.g., subject receipt of a prohibited vaccine or medication that might affect immune response or a medication error with suspected decrease in potency of the vaccine.

- a) The sampling windows with grace period specified in Table 7 will be used to define the valid samples for Immunogenicity Analysis Set.
 - b) The sampling windows per protocol specified in Table 7 will be used to define the valid samples for Immunogenicity Analysis Per Protocol Set.
 - c) In cohort 9 all randomized subjects who have a valid and determinate immunogenicity result from the blood sample and have no other important protocol deviations that can confound immunogenicity data, will be included in the Immunogenicity Analysis Set.
 - d) Participants with missing baseline data will be included in this population, providing other criteria are met
- Abbreviation: IMP = investigational medicinal product.

